### 8.3.2.2. Follow-up

Patients with confirmed PD at the EOT visit will have an safety follow-up of 5 months ( $\pm 15$  days) planned after the last nivolumab infusion, provided no new cancer treatment or end-of-life care has been started, otherwise this visit may be done immediately before if any of these occur. Patients without PD documented at the EOT visit will continue in follow-up for efficacy every 12 weeks ( $\pm 1$ -week window) until PD or start of new treatment or end-of-life care, whichever occurs first. After PD or new cancer treatment or end-of-life care starts, patients will not attend more onsite visits, however, they and/or relatives may be contacted (by telephone, email or mail) every 4 ( $\pm 1$ ) months to update the survival status until the end of the Main study period (18 months have elapsed since the LPI was included in the study or 60 days after LPLV, whichever occurs first).

- Follow-up assessments comprise onsite visits:
- Safety: For all patients, one first safety follow-up visit will be conducted 90 days ( $\pm 15$  days) after last study treatment; a second safety follow-up visit will be scheduled at 5 months ( $\pm 15$  days) after the last nivolumab infusion, provided the first safety follow-up visit did not overlap ( $\pm 1$  week), and if the patient is still alive and no further anticancer treatment has been started yet..
- Efficacy: Patients without evidence of PD at EOT will be assessed for PD by appropriate methods (CT scan or MRI, and clinically) every 12 weeks ( $\pm 1$  week) until symptomatic PD or confirmed iRECIST PD or start of any new cancer treatment or end-of-life care or the end of the Main study period, whichever occurs first. For patients who continue study treatment after the Main study period, tumor response assessments will continue at the frequency of local institutional care practice until PD, start of any new anti-cancer therapy, death or EOT, whichever occurs first.
- Survival calls/contact: All patients alive after symptomatic progression or confirmed iRECIST PD or start of new anti-cancer treatment will be contacted (by telephone, e-mail or mail) every 4 ( $\pm 1$ ) months until the end of the Main study period. In case patients cannot be reached, the primary physician or the patient's partner or family may be contacted by the Investigator or designee.

The following scheme summarizes the temporal relationship between EOT and EOS:

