#### **11.4.1. Derived parameters and endpoints**

##### **11.4.1.1. Efficacy**

Patients without any new anticancer therapy or PD will be assessed for anti-tumor efficacy every 8 weeks (±1 week) during the first 10 cycles and then every 12 weeks (± 1 week) from Cycle 13 onwards until PD occurs or start of a new cancer treatment or end-of-life-care or until the end of the Main study period whichever occurs first. For patients who continue study treatment after the Main study period, tumor

response assessments will continue at the frequency of local institutional care practice until PD, start of any new anti-cancer therapy, death or EOT, whichever occurs first.

Response according to RECIST version 1.1 (38) or GCIG criteria (39) (Cohort 4 for RECIST non-evaluable patients) will be assessed in the efficacy and ITT populations. CR and PR must be demonstrated by objective tumor assessment (CT scan/MRI or CA-125 dosage) and confirmed 4 weeks later. All patients will have a CT scan/MRI or CA-125 dosage at the time of PD. Tumor response will also be assessed by using the novel modified RECIST v1.1 guideline for immunotherapeutics, iRECIST.(40) These exploratory analyses using iRECIST guideline will be presented in detail in the SAP.

In case of premature discontinuation with SD at the EOS visit, this SD will be included in the derivation of efficacy parameters only if the assessment has been performed at least 35 days after treatment start.

The start of a systemic new anti-cancer therapy without prior disease progression could potentially impact the tumor activity observed, hence potentially biasing the evaluation of Debio 1143 anti-tumor activity. As a consequence, no further efficacy data will be collected after the start of any new anti-cancer treatment, except for OS, at least until study data cut-off.

The confirmed response will be used in the primary ORR analysis while a secondary analysis will be performed using the unconfirmed response.

- **Objective response** is derived as any PR or CR recorded after the start of study treatment until disease progression/recurrence is documented, a new systemic anti-cancer therapy is started or analysis cut-off, whichever occurs first.
- **BOR** is the best response (CR, PR, stable disease or disease progression) recorded after the start of study treatment until disease progression/recurrence is documented, a new systemic anti-cancer therapy is started or analysis cut-off, whichever occurs first.

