- **Disease control** is derived as any CR, PR or stable disease reported during the study
- **Duration of response** is the time from documentation of tumor response to disease progression, start of a systemic new anti-cancer therapy or analysis cut-off, whichever occurs first.
- **PFS duration** is defined as the time elapsed between treatment initiation and tumor progression or death from any cause, whichever occurs first. Censoring to the last assessment will be applied in the following situations: a) lost to follow-up, b) no progression before analysis cut-off, c) start of a new systemic anti-cancer therapy. The median PFS and the PFS rate at 6, 12 and 18 months will be derived from the Kaplan-Meier curves.
- **OS** is defined as the time elapsed between treatment initiation and death from any cause. In the main analysis, censoring to the last assessment will be applied in the following situations: a) lost to follow-up, b) alive at analysis cut-off. A sensitivity analysis will be performed by censoring the OS at the time of start of a new systemic anti-cancer therapy. The median OS and the OS rate at 12 months will be derived from the Kaplan-Meier curves.

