17.2.1.5. Progression-free survival (PFS)

PFS (months) is defined as (date of the first documented disease progression or death due to any cause, whichever occurs first – start date of treatment + 1)/30.4375.

The following censoring rules will be applied:

Situation	Date of Progression or Censoring	Outcome
No baseline and/or no post baseline assessment	Date of first dose	Censored
Disease progression documented between scheduled visits	Date of disease progression	PFS event
Death due to COVID-19	Date of last adequate assessment	Censored
Death before first assessment	Date of death	PFS event
Death between adequate assessment visits	Date of death	PFS event
New systemic therapy started prior to disease progression	Date of last adequate assessment* prior to the start of subsequent antineoplastic therapy	Censored
Treatment discontinuation for undocumented disease progression after the last adequate assessment	Date of last adequate assessment	Censored
No documented disease progression or death	Date of last adequate assessment	Censored

For patients in cohort 4, not evaluable by RECIST so being assessed by CA-125 criteria, the below table describes the criteria for defining progression and the date to be used in PFS derivation.

GCIG-Rustin-modified definition of progressive disease according to CA-125 definition		
	Definition of progression	Date of progression
Patients with elevated CA-125 before treatment and normalisation of CA-125 during treatment	CA-125 \geq 2 X ULN documented on 2 occasions**	Date CA-125 is first elevated to \geq 2 X ULN
Patients with elevated CA-125 pre-treatment that never normalises	CA-125 \geq 2 X nadir value on 2 occasions**	Date CA-125 is first elevated to \geq 2 X nadir value

Document: T:\sas\Debiopharm\Debio_1143\CZA60507\Biostatistics\Documentation\SAP\SAP Text\5
 Author: [REDACTED] Version Number: 5.0
 Version Date: 19APR2022

Template No.: CS_TP_BS016 Revision 5 Reference: CS_WI_BS005
 Effective Date: 01Apr2018

Copyright © 2009, 2010, 2012, 2016, 2018 IQVIA. All rights reserved. The contents of this document are confidential and proprietary to IQVIA Holdings Inc. and its subsidiaries. Unauthorized use, disclosure or reproduction is strictly prohibited.

Patients with CA-125 in normal range pre-treatment	CA-125 ≥ 2 X ULN documented on 2 occasions**	Date CA-125 is first elevated to ≥ 2 X ULN

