17.2.1.6. Duration of response (DoR)

DoR (months) is defined as (date of the first documented disease progression or death due to any cause, whichever occurs first – date of the initial response (PR or CR) or date of first reduction of 50% in CA-125 + 1)/30. 4375. It will be calculated only for subjects with a uBOR of CR/PR or at least a 50% reduction in CA-125 levels from a pre-treatment sample. Subjects that are lost-to-follow-up before disease progression will be censored at the date of their last adequate tumour assessment (i.e. a tumour assessment not showing NE) that occur before the start of a new anti-neoplastic therapy.

The median DoR and the DoR rate will be derived from the Kaplan-Meier curves, as described in section 7.6.

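### SAP 17.2.1.6 has no censoring rule for a responder who starts a new therapy without progression, so read literally a later death is the duration-of-response event

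*SAP*

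**What the plan says.** SAP 17.2.1.6 computes DoR in months from "date of the first documented disease progression or death due to any cause, whichever occurs first – date of the initial response (PR or CR", or from the first 50% fall in CA-125. It is calculated for patients whose unconfirmed best response is CR or PR, or who have the CA-125 fall. The section has one censoring sentence: "Subjects that are lost-to-follow-up before disease progression will be censored at the date of their last adequate tumour assessment". The sentence closes by restricting those assessments to ones "that occur before the start of a new anti-neoplastic therapy". SAP 17.2.2 adds nothing; it refers back to 17.2.1 for censoring.

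Protocol 11.4.1.1 defines DoR as the "time from documentation of tumor response to disease progression, start of a systemic new anti-cancer therapy or analysis cut-off, whichever occurs first". Death is not named there. The same section says that "no further efficacy data will be collected after the start of any new anti-cancer treatment, except for OS".

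The PFS censoring table in SAP 17.2.1.5 has a row headed "New systemic therapy started prior to disease progression", which censors at the last adequate assessment before that therapy. It also has a row that censors patients with no progression or death. SAP 17.2.1.6 does not refer to this table. SAP 4.3, which lists changes from the protocol, does not mention DoR.

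**The concern.** The protocol itself foresees patients who start a new systemic therapy without prior progression, and warns that this could bias the evaluation of anti-tumour activity. For such a responder tumour data stop but survival data continue, so death is the one DoR end event still being collected. If the SAP's rule is programmed as worded, survival on the next treatment is reported as response to Debio 1143 plus nivolumab, and a patient's DoR can be longer than the same patient's PFS. DoR is a secondary endpoint in both parts and is read beside the response rate.

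**Working it through.** The plan states no figure that rests on this rule, so there is nothing to reproduce. The check compares the texts and then works through one record.

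**1. Is this patient lost to follow-up?** No. Protocol 8.3.2.2 says: "All patients alive after symptomatic progression or confirmed iRECIST PD or start of new anti-cancer treatment will be contacted", every 4 (±1) months until the end of the Main study period. The protocol's PFS definition in 11.4.1.1 also lists loss to follow-up and start of a new systemic therapy as separate censoring situations.

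**2. What each rule does with a responder who starts new therapy without progression and later dies**

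| Place | Result |
|---|---|
| SAP 17.2.1.6 (DoR) | Event at death |
| SAP 17.2.1.5 (PFS) | Censored at the last adequate assessment before the new therapy |
| Protocol 11.4.1.1 (DoR) | Stops at the start of the new therapy |
| SAP 17.2.1.2 and 17.2.1.3 (best response) | Nothing after the new therapy counts |

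If this patient is still alive at cut-off, SAP 17.2.1.6 gives no rule at all. The same is true of a responder still in response at cut-off.

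**3. Worked record (dates assumed).** First dose 1 Jan 2020, PR 12 Feb 2020, last scan still PR 3 Jun 2020, new therapy 1 Jul 2020, death 1 Jul 2021. The SAP formula is (end date − start date + 1)/30.4375.

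- DoR, SAP as worded: (505 + 1)/30.4375 = 16.62 months, event
- DoR, protocol stop: (140 + 1)/30.4375 = 4.63 months
- DoR, PFS-style rule: (112 + 1)/30.4375 = 3.71 months, censored
- PFS, SAP: (154 + 1)/30.4375 = 5.09 months, censored

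So 16.62 − 4.63 = 11.99 months on the next therapy are counted as response, and DoR is 16.62/5.09 = 3.3 times PFS.

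**4. Other survival times.** Take a second assumed record: response on day 57, last scan on day 169, new therapy on day 180. Death on day 240, 400 or 540 gives a DoR event at 184/30.4375 = 6.05, 344/30.4375 = 11.30 or 484/30.4375 = 15.90 months. The part after the new therapy is 1.97, 7.23 or 11.83 months. The PFS-style rule gives 113/30.4375 = 3.71 and the protocol stop 124/30.4375 = 4.07 in every case. PFS is 169/30.4375 = 5.55, so even the earliest death puts DoR above PFS.

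**5. Direction of the median.** Add two assumed responders to the patient in step 3.

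- Progression at 3 and 18 months. As worded, events fall at 3, 16.62 and 18, survival is 2/3 then 1/3, and the median is 16.62. With censoring at 3.71, survival is 2/3 at 3 and 0 at 18, and the median is 18. Correcting the rule lengthens it.
- Progression at 5 and 18 months. As worded, the median is again 16.62. With censoring at 3.71, survival is 1/2 at 5 and 0 at 18, and the median is 5, or 11.5 if the midpoint of 5 and 18 is taken. Correcting the rule shortens it.
- If the patient is the only responder, the median is 16.62 as worded and not estimable once censored.

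**The case against.** The best defence is that the SAP's authors meant to censor. The closing words of the sentence, limiting assessments to those before a new therapy, have little purpose otherwise. SAP 17.2.2 points to 17.2.1 as a whole, which contains the PFS row, and a patient without further scans could be called lost to tumour follow-up. This stands as evidence of intent. It does not supply the rule: the clause only selects the date for patients already classed as lost to follow-up, and the protocol treats that as a different situation from new therapy.

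The affected patient is also uncommon. The protocol asks for an efficacy assessment at progression or treatment discontinuation (8.2.1), and SAP 17.1 accepts clinical progression on the End of Treatment form as progression, so many patients who deteriorate will have an event before any new therapy. That is right, and it limits the size of the point.

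Two stronger readings are tempting, and the documents support neither. A reader might infer that the rule inflates the reported median DoR. It overstates the individual value, but it also turns a censored time into an event, so the median can go either way. A reader might also take four responders in 15, the efficacy boundary, as the DoR sample. That boundary counts confirmed responders in a non-futile cohort, whereas DoR uses unconfirmed responders and SAP 4.3 records the Part B cohorts as futile.

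**Conclusion.** The gap is real as worded. SAP 17.2.1.6 departs from the protocol definition and from the SAP's own handling of PFS and best response, and the departure is not declared. For an affected patient DoR is overstated by the survival time on the next therapy: about 2 to 12 months in the records above, whose dates are assumptions and show the arithmetic rather than a likely frequency.

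Few patients are likely to be affected. A cohort stopped for futility had no unconfirmed response in 8 evaluable patients, or at most one in 11, at that assessment. For the same reason one such patient could be a cohort's whole DoR result. DoR is descriptive, there is no formal hypothesis testing, and no futility or efficacy rule uses it, so no trial decision changes.

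**What to change.** In SAP 17.2.1.6, apply the censoring rows of 17.2.1.5 to DoR:

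- new systemic anti-cancer therapy before documented progression: censor at the last adequate assessment before that therapy;
- no progression or death at cut-off: censor at the last adequate assessment;
- count progression or death as an event only if it comes before any new therapy.

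State as well whether the PFS table's row for COVID-19 deaths carries over to DoR.

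This is still not the protocol's rule, which stops at the start of the new therapy and does not name death. SAP 4.3 should therefore record both remaining differences: the censoring date, and death as an event.

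The cost is a sentence or two in 17.2.1.6, one entry in 4.3 and reuse of the PFS censoring code. The reported median may become shorter, longer or not estimable.

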17.2.1.7. Overall survival (OS)

OS (months) is defined as (date of death due to any cause – the start date of treatment +1)/30. 4375. Subjects with no documented death will be censored at the last date known to be alive (i.e. latest date collected in the eCRF).

The median OS and the OS rate at 12 months will be derived from the Kaplan-Meier curves, as described in section 7.6.

17.2.1.8. CA-125 results

The CA-125 are collected on the tumor marker eCRF for cohort 4 only.

Document: T:\sas\Debiopharm\Debio_1143\CZA60507\Biostatistics\Documentation\SAP\SAP Text\V5	Version Number: 5.0
Author: ██████████	Version Date: 19APR2022

Template No.: CS_TP_BS016 Revision 5
 Effective Date: 01Apr2018

Reference: CS_WI_BS005

17.2.2. MISSING DATA METHODS FOR SECONDARY EFFICACY VARIABLES

No imputation methods will be applied to the secondary efficacy variables. All details regarding how to handle lack of tumour assessment data and censoring is described in section 17.2.1

17.2.3. ANALYSIS OF SECONDARY EFFICACY VARIABLES

17.2.3.1. Analysis of uORR

The uORR will be presented with absolute and relative frequencies in each cohort separately. No homogeneity test will be performed. This analysis will only be carried out for fertility monitoring analyses.

17.2.3.2. Analysis of uBOR, cBOR and disease control

uBOR, cBOR and DCR will be presented using contingency tables with absolute and relative frequencies. For part B, exact 95% confidence intervals will also be presented.

A spider plot will be produced showing the percentage change in sum of longest diameters (SOLD) over time. The profiles will continue until PD, death or lost-to-follow up, whichever occurs first. The spider plot will show key milestones such as time of initial response, first appearance of a new lesion and initial RECIST progression. Additionally, the thresholds for PD and PR will be displayed on the plot. For part A, the plot will be displayed by dose level and for part B, by cohort. For part B, a plot will also be produced for each cohort separately.

A waterfall plot will be produced showing the best percentage change in SOLD. The percentage change from baseline (for each patient) and patients having a BOR of CR or PR will be indicated in the plot. Additionally, the thresholds for PD and PR will be displayed on the plot. For part A, the plot will be displayed by dose level and site of primary tumour. For part B, the plot will be displayed by cohort only.

A vertical bar plot will be produced showing the patient's best overall response. For part A, the uBOR will be presented by dose level. For part B, a separate plot will be produced for both uBOR and cBOR and will be presented by cohort.

17.2.3.3. Analysis of PFS, DoR and OS

For time-to-event endpoints, Kaplan Meier (K-M) estimates will be provided and include number and percentage of events/censored, minimum, Q1, median, Q3 and maximum survival time and associated two-sided 95% CI obtained using the Brookmeyer-Crowley method. The progression-free survival rate and two-sided 95% CI at pre-specified time points will also be provided. In this case, Greenwood's formula will be used for the 95% CI.

Document: T:\sas\Debiopharm\Debio_1143\CZA60507\Biostatistics\Documentation\SAP\SAP Text\V5

Author: XXXXXXXXXX Version Number: 5.0
Version Date: 19APR2022

Template No.: CS_TP_BS016 Revision 5
Effective Date: 01Apr2018

Reference: CS_WI_BS005

Additionally, a swimmers plot displaying key milestones will be produced. For each subject, the time from treatment start until end of follow-up will be represented (from treatment start to last date known to be alive or date of death). In addition, the following information will be displayed: SD/PR/CR duration and any period of re-treatment post-PD, time of end of treatment (if applicable) and the time of any dose reductions. For part A, the plot will be displayed by dose level and for part B, a separate graph will be created for each cohort.

17.2.3.4. Analysis of CA-125

Actual values and change from baseline of CA-125 will be summarised by visit.

17.2.4. SENSITIVITY ANALYSIS OF SECONDARY EFFICACY VARIABLES

A sensitivity analysis will be performed by censoring the OS at the time of start of a new systemic anti-cancer therapy.

Another sensitivity analysis will be performed by censoring the OS at the time of death due to COVID-19, if applicable

17.3. EXPLORATORY EFFICACY

17.3.1. EXPLORATORY EFFICACY VARIABLES & DERIVATIONS

17.3.1.1. BOR by iRECIST

After a patient has had an initial overall response of PD using RECIST criteria the patient will be followed-up using iRECIST.

The iRECIST BOR will be defined as the best response using iRECIST criteria across all time points. The order to obtain the iRECIST BOR is the following: iRECIST Complete Response (iCR), iRECIST Partial Response (iPR), iRECIST Stable Disease (iSD), iRECIST Unconfirmed Progressive Disease (iUPD) and iRECIST Confirmed Progressive Disease (iCPD).

The table below gives examples of assignments of iRECIST BOR:

Document:	T:\sas\Debiopharm\Debio_1143\CZA60507\Biostatistics\Documentation\SAP\SAP Text\V5	Version Number:	5.0
Author:	██████████	Version Date:	19APR2022
Template No.:	CS_TP_BS016 Revision 5	Reference:	CS_WI_BS005
Effective Date:	01Apr2018		

	Timepoint response 1	Timepoint response 2	Timepoint response 3	Timepoint response 4	Timepoint response 5	iBOR
Example 1	iCR	iCR, iPR, iUPD, or NE	iCR, iPR, iUPD, or NE	iUPD	iCPD	iCR
Example 2	iUPD	iPR, iSD, or NE	iCR	iCR, iUPD, or NE	iCR, iPR, iSD, iUPD, iCPD, or NE	iCR
Example 3	iUPD	iPR	iPR, iSD, iUPD, or NE	iPR, iSD, iUPD, NE, or iCPD	iPR, iSD, iUPD, NE, or iCPD	iPR
Example 4	iUPD	iSD or NE	iPR	iPR, iSD, iUPD, or NE	iPR, iSD, iUPD, iCPD, or NE	iPR
Example 5	iUPD	iSD	iSD, iUPD, or NE	iSD, iUPD, iCPD, or NE	iSD, iUPD, iCPD, or NE	iSD
Example 6	iUPD	iCPD	Any	Any	Any	iCPD
Example 7	iUPD	iUPD (no iCPD)	iCPD	Any	Any	iCPD
Example 8	iUPD	NE	NE	NE	NE	iUPD

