### 3. Comparison of RECIST 1.1 and iRECIST§

	RECIST 1.1	iRECIST
Definitions of measurable and non-measurable disease; numbers and site of target disease	Measurable lesions are $\geq$ 10 mm in diameter ( $\geq$ 15 mm for nodal lesions); maximum of five lesions (two per organ); all other disease is considered non-target (must be $\geq$ 10 mm in short axis for nodal disease)	No change from RECIST 1.1; however, new lesions are assessed as per RECIST 1.1 but are recorded separately on the case report form (but not included in the sum of lesions for target lesions identified at baseline)
Complete response, partial response, or stable disease	Cannot have met criteria for progression before complete response, partial response, or stable disease	Can have had iUPD (one or more instances), but not iCPD, before iCR, iPR, or iSD
Confirmation of complete response or partial response	Only required for non-randomised trials	As per RECIST 1.1
Confirmation of stable disease	Not required	As per RECIST 1.1
New lesions	Result in progression; recorded but not measured	Results in iUPD but iCPD is only assigned on the basis of this category if at next assessment additional new lesions appear or an increase in size of new lesions is seen ( $\geq$ 5 mm for sum of new lesion target or any increase in new lesion non-target); the appearance of new lesions when none have previously been recorded, can also confirm iCPD

Independent blinded review and central collection of scans	Recommended in some circumstances—eg, in some trials with progression-based endpoints planned for marketing approval	Collection of scans (but not independent review) recommended for all trials
Confirmation of progression	Not required (unless equivocal)	Required
Consideration of clinical status	Not included in assessment	Clinical stability is considered when deciding whether treatment is continued after iUPD §

“i” indicates immune responses assigned using iRECIST. RECIST=Response Evaluation Criteria in Solid Tumors. iUPD=unconfirmed progression. iCPD=confirmed progression. iCR=complete response. iPR=partial response. iSD=stable disease.

§ Reproduced from Seymour et al, 2017 (40)

Signature Page for document [REDACTED] | Study Debio 1143-106  
Title: Debio 1143-106 - Protocol v4\_incl. Amdt 3\_03Apr2020

Reason for signing: Approved	Name: [REDACTED] Role: [REDACTED] Title: [REDACTED] Date of signature: 03-Apr-2020 06:04:24 GMT+0000
------------------------------	--

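### The SAP's iRECIST best-response order can never return confirmed progression, contrary to its own Examples 6 and 7

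*SAP*

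**What the plan says.** SAP 17.3.1.1 (BOR by iRECIST) opens with when iRECIST is used: "After a patient has had an initial overall response of PD using RECIST criteria the patient will be followed-up using iRECIST". The definition follows: "The iRECIST BOR will be defined as the best response using iRECIST criteria across all time points". The order then given is iCR first, iPR second, and after those "iRECIST Stable Disease (iSD), iRECIST Unconfirmed Progressive Disease (iUPD) and iRECIST Confirmed Progressive Disease (iCPD"). NE is not in the order, although SAP 17.2.1.2 includes it for RECIST BOR.

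Eight worked examples follow. Two of them end in iCPD:

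- "Example 6 iUPD iCPD Any Any Any iCPD"
- "Example 7 iUPD iUPD (no iCPD) iCPD Any Any iCPD"

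Protocol Appendix C, part 3, compares RECIST 1.1 with iRECIST. It lists confirmation of progression as required under iRECIST. On new lesions it says: "Results in iUPD but iCPD is only assigned on the basis of this category if at next assessment additional new lesions appear". On which responses may count it says: "Can have had iUPD (one or more instances), but not iCPD, before iCR, iPR, or iSD".

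SAP 17.3.2 uses the result in a contingency table and as a label on an alternative spider plot. Protocol 8.1.3 and SAP 3.3 class the endpoint as exploratory.

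**The concern.** A definition that takes the best category seen must not rank a prerequisite above the state that it leads to. Here iUPD is the step through which every iCPD passes, and it is ranked as the better result. A patient whose progression is confirmed has both on record, and the literal rule picks iUPD. The examples directly below the rule say otherwise.

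The definition also counts all time points without stopping at iCPD. The last two columns of Examples 6 and 7 (and the third of Example 6) are *Any*, and the answer is still iCPD, so the examples assume a stop that the rule does not state. Appendix C likewise excludes a response recorded after iCPD.

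At stake is the split between confirmed and unconfirmed progression in the iBOR table. That split is what iRECIST adds to RECIST 1.1 on the progression side. Two programmers, one following the sentence and one following the examples, could each defend a different table.

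**Working it through.** **Inputs.** The rule, the order and the eight examples come from SAP 17.3.1.1. The requirement that an iUPD precede an iCPD comes from Protocol Appendix C, part 3. *Any* is taken as one of six values: iCR, iPR, iSD, iUPD, iCPD, NE. NE is ignored when a better category exists, as Example 8 implies.

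**Step 1: the literal rule against the examples.** iBOR is the highest-ranked category among the five time points. Examples 1 to 5 and 8 reproduce in every sequence they allow. Examples 6 and 7 do not.

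Example 6 has three free visits, so 6³ = 216 sequences:

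- at least one iCR: 216 − 5³ = 91, giving iCR
- no iCR, at least one iPR: 125 − 4³ = 61, giving iPR
- neither, at least one iSD: 64 − 3³ = 37, giving iSD
- the remaining 27 give iUPD, because time point 1 is iUPD
- iCPD: 0 of 216, against the tabulated iCPD

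Example 7 has two free visits, so 6² = 36 sequences: iCR 36 − 25 = 11, iPR 25 − 16 = 9, iSD 16 − 9 = 7, iUPD 9, iCPD 0 of 36.

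**Step 2: is this special to the examples?** There are 4,400 five-visit sequences in which the first iCPD, if any, has an earlier iUPD. Of these, 5⁵ = 3,125 contain no iCPD, leaving 1,275 that do. The literal rule gives iCPD in none of the 1,275.

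**Step 3: which change repairs it?**

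| Rule | Example 6 gives iCPD | Example 7 gives iCPD |
|---|---|---|
| As written | 0/216 | 0/36 |
| Rank iCPD above iUPD only | 27/216 | 9/36 |
| Stop at first iCPD only | 0/216 | 0/36 |
| Both changes | 216/216 | 36/36 |

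With the order alone changed, a later iCR, iPR or iSD still wins. With the stop alone, iUPD wins every time. With both, all eight examples reproduce in every sequence. These fractions count possible sequences and are not estimates of how many patients would be affected.

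**Step 4: does another reading of the time points rescue the rule?** If only visits strictly after the first iUPD counted, Example 6 would give iCPD in 8 of 216 sequences (each free visit iCPD or NE, 2³ = 8), and Example 7 still in 0 of 36. Example 8 would become NE instead of the tabulated iUPD. Examples 2 to 8 also list iUPD as their first counted time point, so this reading does not fit.

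**Step 5: responses before progression.** Example 1 reads: "Example 1 iCR iCR, iPR, iUPD, or NE iCR, iPR, iUPD, or NE iUPD iCPD iCR". The iCR at time point 1 is kept although progression follows. If only visits from the first iUPD onwards counted, Example 1 would give iCR in 1 of its 16 sequences (14 iUPD, 1 iPR). The SAP's own table therefore speaks against discarding earlier responses.

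**The case against.** The strongest reply is that the examples sit next to the rule and show what is meant, so a careful programmer would get iCPD right. That is plausible, but the sentence is the definition and the table only illustrates it. Protocol 8.2.1 and 11.4.1.1 defer the iRECIST detail to the SAP, so nothing else settles the conflict.

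A second reply is that responses after iCPD are largely hypothetical, because Protocol 8.2.1 and the imaging footnote to Table 8-6 end scheduled imaging at confirmed iRECIST PD or earlier. This stands: the missing stop should seldom change a result. It still has to be stated, because the examples cannot be derived without it and SAP 7.4 admits unscheduled tumour assessments.

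A third reply is low materiality. This also stands. The primary endpoint and the futility rule use RECIST 1.1 or GCIG, and the counts of iCR, iPR and iSD do not change when iUPD and iCPD swap places.

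A reader might go further and infer that starting iRECIST after RECIST PD loses earlier responses, so that a patient with PR and then PD is scored iUPD. The documents do not establish this. The opening sentence is about follow-up, the definition covers all time points, and Example 1 keeps a response that precedes progression. What remains is a tension between the opening sentence and Example 1: the SAP does not say how a RECIST CR, PR or SD before PD carries over, or what iBOR a patient who never progresses receives.

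**Conclusion.** The point holds as an internal inconsistency. Under the stated order iCPD is unreachable, and Examples 6 and 7 cannot be obtained. The patients misplaced are those with confirmed progression and no iCR, iPR or iSD, who would be shown as iUPD; in the rare case of a response recorded after iCPD, they would be shown in that better category. How many there are cannot be worked out from the documents. The conclusion rests on an iUPD preceding every iCPD, which Appendix C and all of the SAP's examples support.

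Three larger consequences might be inferred and do not follow:

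- **Treatment decisions.** Protocol 8.3.2.1 refers to confirmed progression as it occurs during the study, not to this end-of-study derivation.
- **All confirmed progressions becoming unconfirmed.** A patient with iSD before iUPD and iCPD is scored iSD under the present rule and under the fix.
- **Loss of all sight of confirmed progression or of response after first progression.** SAP 17.3.2 also lists the iRECIST overall responses and runs the alternative spider plot to iCPD.

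The effect is confined to the exploratory iBOR table and the spider-plot labels. Severity: minor.

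**What to change.** In SAP 17.3.1.1, replace the ordering sentence with a rule of this form: iBOR is the best of iCR, iPR and iSD recorded before the first iCPD; if there is none, it is iCPD when an iUPD was confirmed, iUPD when it was not, and NE otherwise. This makes both changes that step 3 shows to be necessary and gives NE a place.

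As a clarification only, add that RECIST CR, PR and SD before RECIST PD count as iCR, iPR and iSD, including for patients who never progress. This brings the opening sentence into line with Example 1.

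The cost is a few sentences of SAP text and a change to the derivation code. No new data are needed: SAP 17.3.2 already lists the overall response by RECIST and by iRECIST from their eCRF pages. The eight examples can stay as they are and serve as test cases for the program.
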